4 STUDY POPULATION

4.1 Selection of Study Population

Male Caucasian patients with a confirmed diagnosis of HIV infection AND continuous cART treatment >4 years AND concurrent HIV RNA <50 copies/mL >3.5 years AND **CD4+ count <400 cells/ μ L** >3.5 years (aka. INR patients) prior to inclusion will be recruited from the outpatient clinic at the Department of Infectious Diseases, Oslo University Hospital.

For the cross sectional sub-study, male Caucasian persons with a confirmed diagnosis of HIV infection AND continuous cART treatment >4 years AND concurrent HIV RNA <50 copies/mL >3.5 years AND **CD4+ count >600 cells/ μ L** >3.5 years prior to inclusion will be recruited from the outpatient clinic at the Department of Infectious Diseases, Oslo University Hospital. HIV uninfected control individuals will be recruited from men referred to the outpatient clinic at Dep. of Gastroenterology, Oslo University Hospital for cancer screening.

4.2 Number of Patients

Twenty HIV-infected INR patients (cases) will be included in this trial. In addition, 20 HIV infected non-INR patients and 20 HIV negative individuals will be included as controls for the subsidiary cross sectional study.

4.3 Inclusion Criteria

- 1) Subjects may be included as **cases** in the study if they meet all of the following criteria:

- HIV seropositive >4 years.
- Continuous cART >4 years.
- Plasma HIV RNA <50 copies/mL >3,5 years.¹⁾
- CD4+ T cell count <**400 cells/μL** >3.5 years.²⁾
- Male, Caucasian
- Age 25-65
- Signed informed consent and expected cooperation of the patients for the treatment and follow up must be obtained and documented according to International Committee on Harmonization (ICH) Good Clinical Practice (GCP), and national/local regulations.

2) Subjects may be included as **control** subjects in the sub-study if they meet all of the following criteria:

- HIV seropositive >4 years.
- Continuous cART >4 years.
- Plasma HIV RNA <50 copies/mL >3,5 years.¹⁾
- CD4+ T cell count >**600 cells/μL** >3.5 years.
- Male, Caucasian
- Age 25-65
- Signed informed consent and expected cooperation of the patients for the treatment and follow up must be obtained and documented according to ICH GCP, and national/local regulations.

Or if they meet all the following criteria:

- HIV seronegative.
- Male, Caucasian
- Age 25-65

Signed informed consent and expected cooperation of the patients for the treatment and follow up must be obtained and documented according to ICH GCP, and national/local regulations.

¹⁾One single measurement ("blip") of HIV RNA >50 copies/ml accepted.

²⁾One single measurement ("blip") of CD4 >400 cells/μl accepted.

4.4 Exclusion Criteria

Subjects must be excluded from participating in this study if they meet any of the following criteria:

- Plasma hepatitis C (HCV) RNA positive.

- Serum hepatitis B surface antigen (HBsAg) positive.
- Comorbidity of inflammatory bowel disease, coeliac disease or malnutrition.
- Concomitant use of non-steroid anti-inflammatory drugs (NSAID), corticosteroids, disease-modifying antirheumatic drugs, or other anti-inflammatory pharmaceutical substances.
- Concomitant use of antithrombotic pharmaceutical substances
- Regular (weekly) use of any probiotic substance within 3 months prior to inclusion.
- Use of antibiotics within 3 months prior to inclusion.
- Deranged liver function (serum albumin <25 g/L or Child-Pugh ≥10)
- Renal failure (estimated glomerular filtration rate (eGFR) <30 ml/min)
- Heart failure (NYHA class II-IV)
- Intolerance to milk or phenylalanine (INR patients only)
- Any reason why, in the opinion of the investigator, the patient should not participate.

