2 STUDY OBJECTIVES AND RELATED ENDPOINTS

The **primary objective** of this study is to assess the safety of probiotics in cART-treated INR patient with chronic HIV infection.

The **secondary objectives** are to i) explore the biological effects of probiotics in cART-treated INR patient with chronic HIV infection, and ii) investigate differences between cART-treated HIV-infected INR and non-INR patients with regards to gut microbial composition and mucosal barrier function.

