3 OVERALL STUDY DESIGN

[figure not shown]
The primary study is a phase I, single arm, open label, consecutive case series study examining the safety of IDOFORM®Travel in patients with a confirmed diagnosis of HIV infection and continuous cART treatment >4 years and concurrent HIV (ribonucleic acid) RNA <50 copies/mL and CD4+ count <400 cells/μL >3.5 years prior to inclusion. There will be no control arm to the intervention. The primary objective is safety assessment. The secondary objective is exploratory. End points at the termination of the intervention will be compared to the parameters at inclusion. (See chart below.)

Study Period	Estimated date of first patient enrolled:	01.12.2015
	Anticipated recruitment period:	18 months
	Estimated date of last patient completed:	30.11.2017
Treatment Duration:	8 weeks	
Follow-up:	Follow-up terminated at termination of treatment	

In a subsidiary cross sectional case control study, the patients included in the intervention will at baseline (week 0) be compared with individuals with chronic HIV infection and continuous cART >4 years and concurrent HIV RNA <50 copies/mL and CD4+ count >600 cells/μL >3.5 years prior to inclusion, and with

HIV uninfected individuals, both control groups matched to cases with regards to gender, ethnicity, age, and comorbidity

Project scheme

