10.4 Statistical Analysis

Non-parametrical statistics will be applied for all analyses, two-sided tests only. Level of statistical significance defined as $p < 0.05$. Patients with missing values will be excluded from analysis of the parameter where value is missing. This study does not have any additional separate statistical analysis plan.

Primary endpoints: (see section 2.1)

i) Adverse events:

- a. Descriptive presentation of frequencies concurrent to study treatment. No comparative statistical analysis.

ii) Δ plasma HIV RNA load:

- a. Δ defined by changes between end of study (week 8) and baseline (week 0).
- b. Assessed by routine HIV RNA quantification at Dep. of Medical Microbiology, OUH.
- c. H_0 : Eight weeks treatment with probiotics does not change HIV RNA load in INR cART-treated chronic HIV-infected patients.
- d. Analyzed by Wilcoxon signed-rank test.

iii) Δ blood CD4 count:

- a. Δ defined by changes between end of study (week 8) and baseline (week 0).
- b. Assessed by routine CD4 cell quantification at Dep. of Immunology, OUH.
- c. H_0 : Eight weeks treatment with probiotics does not change blood CD4 cell count in INR cART-treated chronic HIV-infected patients.
- d. Analyzed by Wilcoxon signed-rank test.

Secondary endpoints: (see section 2.2)

The statistical analysis strategy is described below. As the efficacy assessments of this study are of exploratory nature, the exact parameters assessed and variable to be analyzed are difficult to predict. The conductance of the statistics may diverge from the planned analyses.

- Alterations are defined by:
 - Changes in *variable* between end of study (week 8) and baseline (week 0) in INR cART-treated chronic HIV-infected patients.

or

- Differences in *variable* between INR cART-treated chronic HIV-infected patients (week 0) (cases) and cART-treated immunological responding chronic HIV-infected patients (controls) and HIV negative subjects (healthy controls).
- Null hypothesis (H_0) will be formulated as:
 - H_{0-1} : Eight weeks treatment with probiotics does not alter the *variable* in INR cART-treated chronic HIV-infected patients.

or

- H_{0-2} : INR cART-treated chronic HIV-infected patients (week 0) (cases), cART-treated immunological responding chronic HIV-infected patients (controls) and HIV negative subjects (healthy controls) have equal *variable*.
- Statistical tests will consist of:

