- Composition of microbiota tentatively analyzed by principle components analysis and Monte Carlo permutation test. Microbiota diversity tentatively analyzed by Shannon index and Simpson reciprocal index.
- For single variable analyses H₀-1s analyzed by Wilcoxon signed-rank test and H₀-2s analyzed by One-way ANOVA with Bonferroni posttests.

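### Milk or phenylalanine intolerance excludes INR cases only, so cases and controls in the cross-sectional gut comparison are selected by different rules, which may introduce a bias, probably small

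*Combined protocol and SAP*

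**What the plan says.** Section 4.4 opens with a rule for everyone: "Subjects must be excluded from participating in this study if they meet any of the following criteria". One item in the list is then restricted to one group: "Intolerance to milk or phenylalanine (INR patients only". No other item carries such a limit, and the control inclusion criteria in section 4.3 do not mention intolerance.

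The INR men have two roles. They receive the product, and under section 3 "the patients included in the intervention will at baseline (week 0) be compared with individuals with chronic HIV infection" and with HIV-uninfected men. Section 5.3 places the first dose two days after the first colonoscopy, so the week 0 material is collected before any exposure. Section 4.2 sets the size of the control side: "20 HIV infected non-INR patients and 20 HIV negative individuals will be included as controls for the subsidiary cross sectional study".

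The secondary objective served by this comparison is to "investigate differences between cART-treated HIV-infected INR and non-INR patients with regards to gut microbial composition and mucosal barrier function". Section 3 describes "both control groups matched to cases with regards to gender, ethnicity, age, and comorbidity" and does not define comorbidity. For single variables, section 10.4 has "H₀-2s analyzed by One-way ANOVA with Bonferroni posttests", with no covariate, restriction or sensitivity analysis for intolerance or diet.

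**The concern.** Limiting the exclusion to men who swallow the capsules makes sense for the intervention study; section 5.1 lists aspartame among the ingredients. That reason does not carry over to a comparison of samples taken before the first capsule. There, the rule means that cases have been cleared of a condition that may bear on diet and the gut, and controls have not.

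Sections 1.3 and 2 want differences in microbiota and barrier function to be read as differences by immunological response. If intolerant men enrol as controls and intolerance alters a measured variable, part of any case-control difference comes from the eligibility rule. Such a component could mimic or mask a true difference, and a larger sample would not shrink it.

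**Working it through.** **Which comparisons are touched**

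- INR against non-INR, and INR against HIV-negative: affected, because the exclusion applies to one side only.
- Non-INR against HIV-negative: not affected by this rule, because neither group is screened on it.
- Week 8 against week 0 within INR men, and all safety endpoints: not affected, because there is only one group.

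**Inputs from the protocol.** There are 20 men per group (section 4.2). Tests are two-sided at 0.05 (section 10.4). Bonferroni over three pairs gives 0.05/3 = 0.0167 per pair. The plan has no power or effect figure for this comparison to reproduce; section 10.1 says a sample size calculation for the secondary objectives is not feasible.

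**Assumed inputs, not in the documents.** Prevalence p of intolerance among eligible controls is 5%, 10% or 20%. The shift d in a measured variable in an intolerant man is 0, 0.5 or 1 SD.

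**Step 1: how many intolerant men.** The expected number per control group is 20p, against 0 among cases by rule. The chance of at least one is 1 − (1 − p)^20.

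| p | Expected per control group of 20 | Chance of at least one |
|---|---|---|
| 5% | 1 | 64% |
| 10% | 2 | 88% |
| 20% | 4 | 99% |

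These chances describe presence, not bias.

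**Step 2: bias.** The control mean moves by p × d. The smallest value is 0 (d = 0, any p) and the largest is 0.20 × 1 = 0.20 SD.

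**Step 3: false positives with no true INR effect.** For 20 against 20 with a common SD, the standard error of the difference is √(2/20) SD, so the noncentrality is p × d × √10. Two-sided t test, 38 degrees of freedom:

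| p × d (SD) | Arises from | Noncentrality | Rejection at 0.0167 | Rejection at 0.05 |
|---|---|---|---|---|
| 0 | d = 0 | 0 | 1.67% | 5.00% |
| 0.025 | 5%, 0.5 SD | 0.08 | 1.70% | 5.07% |
| 0.05 | 5%, 1 SD or 10%, 0.5 SD | 0.16 | 1.79% | 5.27% |
| 0.10 | 10%, 1 SD or 20%, 0.5 SD | 0.32 | 2.18% | 6.10% |
| 0.20 | 20%, 1 SD | 0.63 | 3.85% | 9.46% |

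A normal approximation gives 4.0% and 9.7% in the last row. The 0.0167 column is the relevant one under the planned posttests. The 0.05 column applies only if pairs are tested without correction.

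**Step 4: does anything else in the plan remove the imbalance?** Matching on comorbidity would help if intolerance counted as one, but section 3 does not say so. Medical history is taken at screening for cases and controls (sections 6.1 and 6.2.1), but no intolerance item is specified, and the CRF check boxes listed in section 6.2 cover medication only.

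**The case against.** The best case for leaving the text alone has four parts.

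- **The restriction is deliberate.** Only INR men take the capsules, and barring controls for a product-related reason narrows the control groups. This explains the rule for treated men and supports keeping it for them. It does not explain a different rule in the week 0 comparison.
- **The main gut confounders are already handled alike.** Inflammatory bowel disease, coeliac disease, malnutrition, recent antibiotics and regular probiotics exclude in all groups, and the investigator may exclude for any other reason. This stands, and it limits what intolerance could add.
- **The comparison is exploratory.** Section 10.4 allows the analysis to depart from plan, so leaving out intolerant controls is already permitted. That is true, but it can be done reliably only if intolerance has been recorded.
- **The harm rests on two assumptions stacked together.** This also stands. With no effect on the outcome there is no bias, and only the extreme corner of the range gives a visible inflation.

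A reader might infer that bias is built into the comparison, or that any INR difference would be an artefact of eligibility. The documents do not support that. What is built in is an asymmetry of selection. It becomes bias only if intolerant men enrol as controls and intolerance changes the variable in question. The endpoints range from mucosal microbiota to systemic T-cell signalling, and the criterion pools milk and phenylalanine, so one effect size cannot be presumed for all of them.

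**Conclusion.** The asymmetry is certain from the text; its consequence is not. Cases and controls are selected by different rules on a condition that may affect diet and gut outcomes, and nothing in the matching or the planned test clearly corrects for this.

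Under the assumed ranges (prevalence 5% to 20%, effect 0 to 1 SD, common SD, 20 per group), the bias lies between 0 and 0.20 SD. The per-pair false-positive rate reaches at most about 4% against a nominal 1.7%, or about 9.5% against 5% without correction. It is small unless intolerance is both common and strongly related to the outcome. The point concerns a secondary, exploratory comparison and does not touch the primary safety objective. It is a cheap improvement, not a threat to the trial.

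**What to change.** Apply the intolerance criterion in section 4.4 to all three groups, leaving the rule for treated patients as it is.

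If controls are already enrolled, record milk and phenylalanine intolerance as a specific screening item in all groups, and state in section 10.4 that the H0-2 comparisons will be repeated without intolerant controls. Cases contain none by rule, so this puts both sides on the same footing.

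The cost is one change of wording, one screening question, and a few otherwise eligible controls not enrolled or left out of the repeat analysis. At the assumed prevalences that is 1 to 4 expected per group, leaving 16 to 19 of 20 in the repeat analysis. No sample size or safety figure changes.

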5 TREATMENT

For this study IDOFORM®Travel is the Investigational Product.

5.1 Product Identity, Supply and Storage

IDORORM®Travel capsules contain live *Lactobacillus rhamnosus* GG (LGG®),- *Lactobacillus acidophilus* LA-5®,- *Lactobacillus bulgaricus* LBY-27®,- *Bifidobacterium animalis* subsp. *lactis* BB-12®, and *Streptococcus thermophilus* STY-31® at a total amount of 3 x10⁹ cfu/capsula. Inactive ingredients: xylitol, aspartame, acesulfam K, microcrystalline cellulose, isomalt, mannitol, methylcellulose, inulin fatty acids, silicon dioxide, glucose, aromas, and citric acid. Storage: Room temperature (<25°C, low ambient humidity). Manufacturer: Pfizer A/S. Distributor: Alliance Healthcare Norge AS.

5.2 Dosage and Investigational Product Administration

Four capsules orally every 24 hour (12*10⁹ cfu/day), with or without food or other drugs according to the subject's preference.

IDOFORM®Travel is previously not documented administered to patients with HIV infection. Studies assessing biological effects of probiotics in other diseases strive for high-dose ranges above 10¹⁰ cfu/day. (63, 64)

5.3 Duration of Therapy

First dose is to be taken two days after first colonoscopy and dispensing of capsules.

Therapy shall be continued for eight weeks therapy unless serious adverse events are encountered. Last dose is to be taken at the day of the end-of-protocol colonoscopy.

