1.3 Rationale for the Study, Hypotheses and Purpose

Based on the scientific knowledge presented above we find it warranted to test the following hypotheses:

- i) CART-treated chronic HIV-infected INR patients have an altered composition of their gut microbiota compared with HIV-infected cART-treated immunological responder patients.
- ii) CART-treated chronic HIV-infected INR patients have impaired gut mucosal barrier function compared with HIV-infected cART-treated immunological responder patients, and this dysfunction relates to perturbations in mucosal Th17 and Th22 CD4+ T cells.
- iii) Administration of probiotics to INR cART-treated chronic HIV-infected patients is safe and coincide with alteration of gut microbiota and restoration of mucosal barrier function and reduced systemic immune activation.

To this date there are no scientific publications answering these hypotheses. Exploration of these queries may provide targets for adjuvant therapy in substantial number of patients not responding sufficiently to cART and thereby improve their clinical prognosis.

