Included subjects will perform bowel emptying procedure with Citrafleet® (see also section 5.5.1) starting 20-28 hours in advance of colonoscopy.

Peripheral vein cannula will be inserted in case of peri-procedural need for sedation with midazolam 5-10 mg intravenously according to routine colonoscopy procedures.

Full endoscopic examination will be performed from rectum to terminal ileum. Subsequently, multiple biopsies will be collected in terminal ileum, ascending colon and sigmoid colon will be collected. See section 6.5.3 for further details.

A Standard Operating Procedure (SOP) for the colonoscopy will be produced in Norwegian to ascertain a safe, uniform and reproducible procedure in all study subjects.

Stool samples

Included subjects will immediately before starting bowel emptying sample a tea-spoon size of own stool that they will bring to the upcoming visit and colonoscopy. All included subjects will at screening visit be given a sampling kit for the collection of the stool samples.

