6.5.3 Stool samples

Stool will be sampled by the individual subjects immediately before he starts bowel emptying. Stool sample will be put in buffer-containing. *PSP® Spin Stool DNA sampling tube (Invitex) v01*. The sample tube will be collected by the investigator at colonoscopy visit and stored in -80°C for later nucleic acid-based assays for analysis of microbial composition and function.

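### Week 0 microbiota samples are off product and week 8 samples on it, so the all-taxa tests in section 10.4 can reject H0-1 because of the five administered strains alone

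*Combined protocol and SAP*

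**What the plan says.** All references are to the combined protocol and SAP.

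- **Product.** Section 5.1 names five live strains, "at a total amount of 3 x10⁹ cfu/capsula". Section 5.2 sets four capsules a day.
- **Baseline.** "First dose is to be taken two days after first colonoscopy and dispensing of capsules" (5.3). Week 0 samples therefore precede any product.
- **Week 8.** "Last dose is to be taken at the day of the end-of-protocol colonoscopy" (5.3). Whether that dose comes before or after the biopsies is not stated.
- **Stool.** "Stool will be sampled by the individual subjects immediately before he starts bowel emptying" (6.5.3). Section 6.2 has bowel emptying "starting 20-28 hours in advance of colonoscopy", so week 8 stool is taken about a day before the final dosing day, with dosing still under way. It is read by nucleic acid assays.
- **Biopsies.** Those kept for microbiota are washed in PBS (6.5.2).
- **After treatment.** The flow chart (6.1) places colonoscopy and stool only at weeks 0 and 8. The later contact is a telephone call, at week 10 in 6.1 and week 12 in 6.2.5, while section 3 ends follow-up with treatment. These three passages need reconciling, but none of them includes a sample.
- **Analysis.** Section 10.4 defines alteration as the week 8 versus week 0 change. Composition goes to principal components and a Monte Carlo permutation test. For diversity: "Microbiota diversity tentatively analyzed by Shannon index and Simpson reciprocal index". Single variables go to the Wilcoxon signed-rank test. Nothing says that the five product species are identified, removed or reported apart.
- **Hypothesis.** Hypothesis iii (1.3) is that the probiotic "is safe and coincide with alteration of gut microbiota and restoration of mucosal barrier function".

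**The concern.** The paired contrast is on product against off product. Any product DNA in the week 8 sample enters the measured community at that visit only, so a test on all taxa responds both to a shift in the patient's own bacteria and to organisms he swallowed in the preceding days.

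The microbiota is the first secondary endpoint (2.2) and the first link in the chain that section 1.1 proposes, from microbiota through barrier and T cells to immune activation. If a positive composition test is read as a changed resident community when it reflects only the capsules, that first link looks supported when it is not.

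**Working it through.** **Figures in the documents.** Daily load: 4 × 3×10⁹ = 12×10⁹ cfu, as stated in 5.2. Section 10.1 gives no effect size, SD or power for the microbiota endpoints, so there is no plan figure to reproduce for this point.

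**Inputs.** From the documents: 20 pairs, two-sided 0.05, five strains, product present at week 8 only. Assumed: the product share of reads f (0.1% to 20%), the resident community and the within-patient noise.

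**1. Composition, by simulation with unchanged residents.** 120 resident taxa with no systematic change; 10,000 reads per sample; product absent at week 0; mean share f at week 8, varying between patients; within-patient sign-flip permutation test; 300 runs per setting. Ranges cover a log SD per taxon of 0.3 and 0.6. Entries are the percentage of runs rejecting at 0.05.

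| Mean f | Log-ratio | Hellinger | Raw relative abundance |
|---|---|---|---|
| 0 | 5 | 3-8 | 5-6 |
| 0.1% | 100 | 7-14 | 6 |
| 1% | 100 | 90-100 | 5-6 |
| 5% | 100 | 100 | 14-58 |
| 10% | 100 | 100 | 65-99 |

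The data scale decides the exposure, and 10.4 does not name one.

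**2. Diversity, by formula.** Let H be the resident Shannon index and h(f) = −f ln f − (1−f) ln(1−f). Five equally abundant new taxa change Shannon by −fH + h(f) + f ln 5. One new taxon changes it by −fH + h(f).

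- H = ln 10 = 2.30, f = 5%, five equal strains: −0.115 + 0.199 + 0.080 = +0.164. Reciprocal Simpson goes from 10 to 1/[0.95²/10 + 5(0.01)²] = 11.02.
- H = 3.5, f = 5%, five equal strains: −0.175 + 0.199 + 0.080 = +0.104.
- H = 3.5, one strain: +0.024 at f = 5%, −0.025 at 10%, −0.20 at 20%.
- H = 4.5, f = 20%, five equal strains: −0.078.

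The sign is not fixed.

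**3. Signed-rank rejection for Shannon.** n = 20, normal paired changes, SD of change 0.3 (assumed), five equal strains. Ranges are across repeated simulations.

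| Resident H | f | Shift | Rejection |
|---|---|---|---|
| 2.30 | 5% | 0.164 | 61-62% |
| 2.30 | 2% | 0.084 | 20-22% |
| 2.30 | 1% | 0.049 | about 10% |
| 3.5 | 5% | 0.104 | 29-31% |
| 3.5 | 1% | 0.037 | about 8% |

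With H = 2.30 and f = 5%, the rate is about 93% if the SD of change is 0.2 and about 39% if it is 0.4. In the fuller simulation of step 1, Shannon rejected in 8-13% of runs at f = 1%, 20-53% at 5% and 25-62% at 10%, then 12-24% at 20%, where the mean shift shrinks. Reciprocal Simpson gave 12-22% at 5%.

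**4. Product taxa removed at both visits.** In the step 1 simulation, rejection returns to 3-7% for Shannon and for composition on the Hellinger and log-ratio scales. The one exception is 11% for log-ratio composition at f = 20% with low noise, where fewer resident reads remain.

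**The case against.** **Product presence is itself an alteration.** Neither hypothesis iii nor the definition in 10.4 confines alteration to resident bacteria, and 1.2 describes probiotics as possible colonisers of the gut. This stands. Taken literally, rejecting H0-1 because product is present is not a false positive. The difficulty is what the rejection is then taken to mean, so the all-taxa result should be kept.

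**The main assessment is less exposed.** Section 7.1 lists mucosa-adherent composition and does not list stool. Biopsies follow bowel emptying and a PBS wash, both of which should lower carry-over. This stands in part: the plan does not say that the wash is meant to clear product, and 6.5.3 still collects stool for microbial composition with no such step.

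**The plan is exploratory and tentative.** True, and it limits the weight of the point. But 10.4 says there is no separate analysis plan, so it is the only place to settle this.

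**Stronger readings that the documents do not support.**

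- That no off-product sample exists. Week 0 is off product; only a post-treatment sample is missing.
- That a positive result could never be told apart from swallowed capsules. To the extent that the assay resolves species, the planned reads already hold the information. What is missing is a stated analysis.
- That diversity is pushed the same way in every compliant patient. Step 2 shows shifts of either sign.
- That about 61% is the trial's error rate. It belongs to one assumed scenario.

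**Conclusion.** The point holds as a matter of interpretation. With week 0 off product, week 8 on product and no separation of the five species, the all-taxa comparison can reject H0-1 with the resident microbiota unchanged. Composition is the most exposed: on Hellinger or log-ratio data a 1% share suffices in the simulation, while raw relative abundance is hardly affected at that share. Stool is more exposed than washed biopsies. Diversity is affected less predictably, in size and in direction.

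The sizes rest on the assumed share f, on the simulated community and on product species being absent at baseline. The documents give none of these, although 4.4 excludes regular probiotic use in the prior three months. A reader might infer that the primary safety objective is also compromised. It is not: its endpoints are adverse effects, viral load and CD4 count. The effect is confined to what can be concluded about the first secondary endpoint and hypothesis iii.

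**What to change.** In 10.4, prespecify for the week 0 to week 8 comparison, in stool and biopsies:

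1. Run the composition and diversity analyses on all taxa, and again with reads assigned to the five administered species removed at both visits and the remainder re-normalised. Report the two side by side.
2. Report the product taxa separately, as carriage or exposure.
3. Claim a change in the resident microbiota only if the product-removed analysis also shows it.
4. Where the assay resolves only genus, treat genus-level removal as a sensitivity analysis and nothing more.
5. Name the data scale for the composition test.

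The cost is a paragraph and one more run of the same pipeline, with no change to dosing or sampling. Section 10.3 allows changes to the plan until database lock; because the plan sits inside the protocol, the approval route in 11.3 may apply. The downside is that native members of the same species are lost from the second analysis, which is why the all-taxa result stays beside it.
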